# Inputs
alpha <- 0.05
                            # Significance level
power <- 0.80
                            # Power
percent_improvement <- 0.14 # 14% MCID based on literature
                            # Correlation (r) between baseline and outcome based on pilot sample
correlation <- 0.75
loss_to_follow_up <- 0.033 # Loss-to-follow-up based on pilot sample</pre>
fiqr_baseline_mean <- 57.69444 # Baseline mean based on pilot sample</pre>
fiqr_baseline_sd <- 18.68821</pre>
                                 # Baseline standard deviation based on pilot sample
# Calculate the mean difference for 14% improvement (MCID)
mean_difference <- fiqr_baseline_mean * percent_improvement</pre>
# Calculate Cohen's d for MCID
cohen_d <- mean_difference / fiqr_baseline_sd</pre>
# Function to calculate sample size for t-test
calculate_sample_size_ttest <- function(effect_size, alpha, power) {</pre>
  z_alpha <- qnorm(1 - alpha / 2) # Z-value for two-tailed test</pre>
                                   # Z-value for power
  z_beta <- qnorm(power)</pre>
  n_per_group <- ((z_alpha + z_beta)^2 * 2) / (effect_size^2)</pre>
  return(ceiling(n_per_group))
}
# Calculate sample size for t-test
n_ttest <- calculate_sample_size_ttest(cohen_d, alpha, power)</pre>
# Adjust sample size using N_adjusted = N * (1 - r^2)
n_adjusted <- n_ttest * (1 - correlation^2)</pre>
# Combine groups (total sample size)
n_total_adjusted <- ceiling(2 * n_adjusted)</pre>
# Account for 10% loss to follow-up
n_adjusted_with_loss <- ceiling(n_adjusted / (1 - loss_to_follow_up))</pre>
# Total adjusted sample size (with loss-to-follow-up)
n_total_adjusted <- 2 * n_adjusted_with_loss</pre>
```

3.4 Statistical Interim Analysis, Data Review and Stopping guidelines

No Data Safety and Monitoring Committee (DSMC) was set up for this trial due to the low-risk nature of the intervention studied. There are no formal interim analyses and therefore no formal stopping rules for this study.

3.5 Timing of Analysis

The final analysis of all primary and secondary endpoints will be conducted together when all recruited patients have reached their planned follow-up up to 6 months and the relevant data received, cleaned and finalised.

The trial also includes long-term follow-up from randomisation up to 12-months; the analysis of this data will be reported separately following a separate statistical analysis plan.

3.6 Blinded analysis

A blinded analysis of the data (not separated by treatment arm) will be undertaken after the pilot sample (phase 1) have been recruited to estimate the variability of the outcome measure (FIQR). In addition, a blinded analysis of the data will be undertaken prior to the final data lock to undertake data cleaning, to look into the distribution of variables, missing data distributions, and to review exclusions associated with the per protocol population.

3.7 Statistical Analysis Outline

It is anticipated that all the statistical analysis will be undertaken using R although other well-validated statistical packages, such as Stata, may be considered for statistical quality control validation analyses. All analyses will be carried out under a treatment policy strategy (that is, all participants will be analysed in the group they were randomised to regardless of actual treatment received).

The analyses will be repeated for the *per protocol* population (definition in section 4.2) as mandated by the protocol, bearing in mind that this may introduce bias by losing the benefits of randomisation and introducing ambiguity in the primary estimand of interest.

Although we have allowed for up to 5% missing data in the sample size at 3 months, we hope to minimise this by utilising data collection techniques appropriate to the fibromyalgia patient population. Before carrying out the within trial analysis, we will check the trial data for any missing data. Where possible the reasons for missing data will be ascertained and reported. The nature and pattern of the 'missingness' will be carefully considered — including whether data can be treated as missing at random (MAR). The handling missing data is detailed in section 6.3. Standard descriptive statistics will be used to describe the demographics between the treatment groups reporting means and standard deviations or medians and interquartile ranges as appropriate for continuous variables, and numbers and percentages for binary and categorical variables. All comparative outcomes will be presented as summary statistics and reported together with 95% confidence intervals and all tests will be carried out at a 5% two-sided significance level.

The Fibromyalgia Impact Questionnaire Revised (FIQR) at 3 months is the primary outcome of the study and the primary analysis will compare this between the treatment groups in a linear mixed effects method including all participant data, adjusting for the stratification factors.

Subgroups analyses will be undertaken with the aim of exploring the consistency of treatment effects across important baseline characteristics (Yusuf et al. 1991). These include:

Insomnia with objective short sleep duration: There is evidence that patients with insomnia with *objectively* short sleep duration (<6 hours) may respond differently to CBT-I(Vgontzas et al. 2013; Ballesio et al. 2019). For this subgroup analysis, an interaction between treatment allocation and baseline TST will be fitted to evaluate effect modification by sleep duration prior to randomisation. The continuous measure of TST will be used to maximise power.

Forest plots with 95% confidence interval will be used to present the subgroup analysis results.

Secondary clinical outcomes will be similarly analysed using mixed effects regression, using logistic regression for binary data and linear regression for continuous data. Any subsequent changes in this plan are strongly discouraged. If any changes to this SAP are implemented these will be documented in an updated version of this SAP. Documentation of any such changes will include the rationale for the changes, and when and by whom these were agreed.

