9.2 Number of Participants

Previous work, using the ratio of tender to swollen joints as an indirect marker of central sensitization in patients with either RA or PSA, has shown that on average 43% of patients with low levels of likely central sensitization achieved remission (using DAS-28 remission criteria) compared to 23% in those with high levels of central sensitisation when being treated with either methotrexate or an anti-TNF agent. However a data simulation study showed that, for machine-learning methods, a sample size of 70 times the number of variables allows accurate identification of the data structure (36). Using the seven main variables of pain, fatigue, sleep disturbance, dyscognition, depression, anxiety and function, data for 490 participants, for each condition would be needed, including the feasibility study.

For the feasibility study 80 participants will be recruited in total, with 40 being assessed using MRI. Participants will be randomised on a 1:1 ratio to the intervention and standard care groups. This should provide a large enough sample to inform the practicalities of delivering dCBT-I, MRI assessments, and provide information on recruitment, uptake, and attrition, which will inform the design of the definitive trial. A moderate effect size (Cohen's d >0.3) would be sufficient to accept the result as worth investigating, in order to achieve a meaningful clinical benefit for patients, and in keeping with similar effects of CBT-I on cognitive outcomes in insomnia.

All participants in the Sleep sub-study will be invited to participate in the focus groups. However, it is envisioned that 18 (three groups of six participants) will take part, owing to the time commitment involved.

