3.3 Sample Size

In the pilot phase (phase 1), the mean FIQR at baseline was 57.69 (SD=18.69). At the 3-month post-treatment follow-up, for the overall group, the mean FIQR was 52.24 (SD=19.06). The correlation between baseline and 3-month follow-up FIQR scores was high (r=0.86; 95%CI 0.73 to 0.93).

Using these values, the sample size was estimated to detect a minimum clinically-important difference (MCID) of 14% improvement in FIQR at 3 months (Bennett, Bushmakin, et al. 2009), corresponding to an improvement of 8.08 (Cohen's d=0.43) in this study, equating to a moderate effect size. Assuming a correlation of r=0.75 (the lower bound of the 95% CI for correlation), significance level of 0.05 and 80% power, the estimated sample size required to detect a 14% improvement in FIQR amongst participants in the Sleepio arm compared to the standard care arm using an ANCOVA is 78 participants (39 per group). This calculation includes an adjustment for a 3.33% loss-to-follow-up rate.

The R code used to estimate the sample size is provided below:

```

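### SAP 3.7 claims a 5% missing-data allowance, but N = 78 in SAP 3.3 was built on 3.3% and a code comment says 10%; the effect on power is small

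*SAP*

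**What the plan says.** SAP 3.7, describing the handling of missing data, states: "Although we have allowed for up to 5% missing data in the sample size at 3 months". SAP 3.3, which contains the calculation, states: "This calculation includes an adjustment for a 3.33% loss-to-follow-up rate". The R code in 3.3 sets the loss rate to 0.033 and attributes it to the pilot, but the comment above the inflation step reads "Account for 10% loss to follow-up".

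The calculation targets a 14% improvement on the pilot baseline mean, "corresponding to an improvement of 8.08 (Cohen's d=0.43) in this study", with "significance level of 0.05 and 80% power". It assumes a baseline to 3-month correlation of 0.75 and arrives at 78 participants, 39 per group. The code standardises the difference by the baseline SD. The same section reports that at 3 months, "for the overall group, the mean FIQR was 52.24 (SD=19.06"), and FIQR at 3 months is the primary outcome.

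Protocol 9.2 gives a different total: "For the feasibility study 80 participants will be recruited in total". It justifies that number on feasibility grounds, not by a power calculation.

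**The concern.** One calculation cannot have three loss allowances. A reader of 3.7 would take the stated sample size to have been inflated for 5% missing outcomes, and 3.3 shows that it was not. SAP 1 says the plan will be available alongside the principal papers, so journal readers will see the allowance, the code and the total together.

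A second, smaller matter concerns the same number. In an ANCOVA the residual variance is the variance of the follow-up score times (1 − r²). The matching SD is therefore the one at 3 months, and the SAP reports it as slightly larger than the baseline SD used. Together these affect how much margin 78 has around the 80% power target.

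**Working it through.** **Inputs, all from SAP 3.3.** Baseline mean 57.69444; difference 14% of this = 8.0772; baseline SD 18.68821; 3-month SD 19.06; r = 0.75, so 1 − r² = 0.4375; power 80%; alpha 0.05, two-sided ("z_alpha <- qnorm(1 - alpha / 2) # Z-value for two-tailed test"). Allocation is 1:1 (SAP 3.2).

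**Reproducing 78.**
- d = 8.0772/18.68821 = 0.4322.
- Unadjusted n per arm = 2(1.960 + 0.842)²/d² = 84.03, which the code rounds up to 85.
- 85 × 0.4375 = 37.19.
- 37.19/(1 − 0.033) = 38.46, rounded up to 39 per arm, total 78. This matches exactly.

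**The same code at the other two loss rates.**
- 5%: 37.19/0.95 = 39.15, so 40 per arm, total 80.
- 10%: 37.19/0.90 = 41.32, so 42 per arm, total 84.

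Of the three rates, only 3.3% yields the stated total.

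**Repeating with the 3-month SD.**
- d = 8.0772/19.06 = 0.4238; unadjusted n = 87.41, rounded up to 88; 88 × 0.4375 = 38.5.
- 3.3%: 38.5/0.967 = 39.81, so 40 per arm, total 80.
- 5%: 38.5/0.95 = 40.53, so 41 per arm, total 82.

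**Power of 78.** With m = 39 × (1 − loss) analysed per arm, power = Φ( d/√(2(1 − r²)/m) − 1.96 ).

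| SD | Loss | m per arm | Power |
|---|---|---|---|
| 18.69 (baseline) | 3.3% | 37.71 | 81.0% |
| 18.69 (baseline) | 5% | 37.05 | 80.3% |
| 19.06 (3 months) | 3.3% | 37.71 | 79.5% |
| 19.06 (3 months) | 5% | 37.05 | 78.7% |

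Example, last row: √(2 × 0.4375/37.05) = 0.1537; 0.4238/0.1537 = 2.758; Φ(0.798) = 78.7%.

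**Loss that 78 can absorb under the SAP's SD and r.** Without the intermediate rounding, 84.03 × 0.4375 = 36.76 analysed per arm are needed. 1 − 36.76/39 = 5.7%, so power stays at or above 80% up to about 5.7% loss.

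**A t-based version** of the same ANCOVA power is about one point lower: at 5% loss, 79.2% with the baseline SD and 77.6% with the 3-month SD.

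**The case against.** A reader might infer that 78 has neither a loss allowance nor 80% power. The documents do not support that. The 78 carries the 3.33% stated in 3.3, and under the SAP's own inputs it keeps 80.3% power at 5% loss. The code returns 80 rather than 78 at 5% only because it rounds 84.03 up to 85 before applying 1 − r²; without that step, 36.76/0.95 = 38.70, which is still 39 per arm. This stands: the total was not derived from 5%, but by the normal formula it tolerates 5%.

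A reader might also treat 10% as a planned allowance. The coded value is 0.033 and no prose mentions 10%, so the comment looks like a leftover. The total of 84 should not be read as a requirement.

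Nor is 19.06 the only defensible SD. It comes from both arms combined (SAP 3.3; SAP 3.6 describes the pilot analysis as not separated by arm), so it would include any between-arm difference. If the full 8.08-point effect had been present in the pilot, the within-arm SD would be about √(19.06² − 8.08²/4) = 18.63, and 78 at 5% loss would have about 80.6% power. With no effect it remains 19.06. The figure is therefore an upper reading of the pilot data and, from a pilot planned at 30, an imprecise one.

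It is also tempting to read 3.33% as one loss in 30. The SAP gives neither the number lost nor the size the pilot reached, so nothing here relies on it.

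Finally, if the pilot correlation of 0.86 held, power would be about 95%. That limits the practical consequence but does not reconcile the three rates.

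**Conclusion.** The inconsistency is certain: 5%, 3.33% and 10% are given for one calculation, and only 3.3%, with the baseline SD, produces 78. SAP 3.7 misstates an input and should be corrected.

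The numerical effect is small. Taking 5% literally moves the code's total from 78 to 80. With the 3-month SD the totals are 80 at 3.3% and 82 at 5%, and 78 has 79.5% and 78.7% power, a shortfall of at most about 1.3 points. It would be wrong to call the trial materially underpowered on this ground.

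These figures rest on the normal formula, the 8.08-point difference and r = 0.75. The last needs a caveat: 3.3 calls 0.75 the lower bound of the 95% interval but prints that interval as 0.73 to 0.93. At r = 0.73, 78 with 5% loss would have 77.7% power (baseline SD) or 76.1% (3-month SD). This outweighs the loss-rate question and should be settled in the same revision.

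**What to change.** Choose one of two wording changes.

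- **If 78 is the target:** change 3.7 to the 3.33% actually used, and correct the 10% code comment to match the coded value.
- **If 5% is the intended allowance:** restate 3.3, the code value and the comment at 5%. The SAP's code then returns 80, which agrees with the total in Protocol 9.2.

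In either case, add to 3.3 that power is about 79% for 78 participants with 5% loss if the 3-month SD of 19.06 applies, and say why the baseline SD was used. A total of 80 should not be presented as fully meeting 80% power under that SD: at 5% loss it gives 79.8%, and the SAP's formula asks for 82.

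The cost is SAP wording, with no participants beyond the protocol's planned 80. The downside is a slightly less favourable stated power.

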4. STATISTICAL PRINCIPLES

4.1 Statistical Significance and Multiple Testing

There is a single pre-specified primary outcome, so there is no correction for multiple testing. A significance level of 0.05 will be used, with 95% confidence intervals reported. All secondary analyses will be considered as supporting the primary analysis and will also be analysed using a significance level of 0.05 with 95% confidence intervals. No adjustment for multiple testing will be performed. In the setting of clinical trials, multiplicity adjustment is often inappropriate as it assumes all tested hypotheses are independent and equally relevant, which is rarely the case in this setting (for example, sleep quality, sleep efficiency, subjective dyscognition, and objective sustained attention are likely to be interrelated). Instead, adjustments like the Bonferroni correction can overcorrect, reducing statistical power and potentially obscuring meaningful clinical findings, especially when endpoints are interrelated and when clinical interpretation is more relevant than strict statistical significance(Schulz and Grimes 2005).

4.2 Definition of Analysis Populations

Populations for analysis are defined as follows:

- Intention-to-treat (ITT): all participants analysed in their randomised groups, regardless of actual treatment received. This reflects the primary estimand of interest (treatment policy).
- **Per-Protocol (PP):** participants who received the intervention as intended will be analysed according to the treatment they actually received. Participants will be excluded from the per-protocol population if:
 - They did not receive the treatment allocated through randomisation
 - They did not fully satisfy the eligibility criteria for the study

Blinded review of the protocol deviation data (not separated by treatment arm) which may affect the PP analyses will be undertaken prior to the final data lock. A summary of the characteristics of exclusions to define the per-protocol population will be reported. The motivation for any such exclusion is to examine the robustness of inferences to factors that can threaten the study's internal validity. Deviations associated with intercurrent events which occurred in the trial setting but would not be observed in practice are considered the main threat, consistent with the primary ITT estimand. If a significant number of such deviations are present e.g. involving more than >5% of participants, the results of the primary analyses may introduce ambiguity in the interpretation. In this case sensitivity analyses is undertaken and detailed in section 6.4.

5. TRIAL POPULATION AND DESCRIPTIVE ANALYSES

5.1 Representativeness of Study Sample and Patient Throughput

A CONSORT flow diagram (**Figure 1**) will be used to summarise the flow of participants through each stage of the trial, including a breakdown of the number of participants in each stage of the trial from screening through recruitment to the end of the trial. The number participants who are excluded, declined consent, withdrew or were lost to follow-up are also summarised in the flow chart.

Figure 1 The PainLESS CONSORT flow diagram

Additional expansion of reasons and timing of withdrawals from the study will be included as needed as in **Table 2** below.

Table 2: Reasons for exclusion

Reason for exclusion	Ν
Not meeting inclusion criteria	
No sleep problems	
No brain fog	
Untreated sleep disorder apart from insomnia	
Nightshift worker	
Prescribed regular sedative medications	
No fibromyalgia diagnosis	
Other medical contraindication (e.g. epilepsy)	
Other	
Total ineligible	
Eligible but refused	
Patient does not want to be part of the research project	
Participant does not want to complete the questionnaires	
Participant does not want to attend baseline study visit	
Patient decision – no reason given	
Other	
Other	
Technical difficulties	
Research staff not available/informed	
Other	
Total eligible but not randomised	
Total patients screened but not randomised	

5.2 Withdrawal from treatment and/or follow-up

The numbers and percentages of participants who are lost to follow-up or withdraw will be reported by treatment allocation for each time point until the end of follow-up at 12 months post-randomisation. Reasons for withdrawal will also be summarised by treatment allocation in **Table 3a** and **Table3b**.

Table 3a: Summary of withdrawals and losses to follow from baseline to 12 months' post-randomisation. For the purpose of this report, a participant is considered to be lost to follow-up at a particular visit if the primary outcome assessments following that visit are all missing.

	dCBT-I and sleep hygiene				Sleep hygiene only			
Totals	Withdrawals	%	Lost-to-follow-up	%	Withdrawals	%	Lost-to- follow-up	%
Baseline								
3 months								
6 months								
12 months								

Table 3b: Summary of reasons for withdrawal by treatment allocation

Reason for withdrawal	dCBT-I and sleep hygiene		Sleep hygiene only		Total	
	N	%	N	%	N	%
Total withdrawn						
Patient does not want to be part of study						
Participant does not want to complete questionnaires						
Participant does not want to attend study visit						
No reason given						
Other reason						

5.3 Baseline Characteristics

Baseline characteristics will be reported by treatment group, including the stratification/minimisation factors and important prognostic, demographic and clinical covariates, as outlined below in **Table 4**.

Numbers (with percentages) for binary and categorical variables and mean (and standard deviation), or median (with lower and upper quartiles) for continuous variables will be presented; there will be no tests of statistical significance nor confidence intervals for differences between randomised groups on any baseline variable.

	dCBT-I		Sleep Hygie	ene	Total	
Continuous	Mean	SD	Mean	SD	Mean	SD
Age, years						
FIQR						
SF36 Bodily Pain Scale						
ISI						
BC-CCI						
Sleep duration, hours [actigraphy]						
Time in bed, hours [actigraphy]						
Sleep efficiency, % [actigraphy]						
PHQ-9						
GAD-7						
ТЅК						
EQ-5D-5L utility						
EQ-5D-5L VAS						
Categorical	N	%	N	%	N	%
Gender						
Male						
Female						
Education						
Higher Degree						

Table 4. Baseline characteristics of participants

No higher degree			
Employment			
Employed			
Not employed			
MRI scan			
Yes			
No			

5.4 Unblinding

All cases of unblinding will be listed, together with who was unblinded, reasons for unblinding and summarised (numbers, percentages).

5.5 Treatment Compliance with Details of Intervention

The intervention groups in this trial are dCBT-I and sleep hygiene advice, or sleep hygiene advice only, in adults with fibromyalgia. All participants will be given sleep hygiene advice at the baseline visit. Compliance for dCBT-I is defined by the proportion of participants who complete each of the 6 sessions of dCBT-I. A complier will be defined as a participant who completes at least 3 of the 6 sessions, as session #3 contains sleep restriction therapy, the core component of CBT-I. The numbers and percentages of participants receiving each treatment are summarised, as well as those who did not receive the allocated treatment. Reasons are given in the cases where the participants did not receive the allocated treatment (**Table 5a**). The numbers and percentages of participants in the dCBT-I arm who access, and complete, each session are summarised (**Table 5b**).

Treatment received	dCBT-I and sleep	hygiene	Sleep hygiene only	
	N	%	N	%
Allocated treatment				
Other				
Reason for not receiving allocated treatment				
Participant decision				
Administrative decision				
Other				

Table 5a. Compliance with allocated intervention

Table 5b. Compliance with dCBT-I among intervention group

	Session	Accessed session	Completed session
--	---------	------------------	-------------------

	N	%	N	%
Session 1				
Session 2				
Session 3				
Session 4				
Session 5				
Session 6				

5.6 Reliability

To ensure consistency, validation checks of the data will be conducted. This will include checking for duplicate records, checking the range of variable values and validating potential outliers where possible. As the data is collected electronically via *REDCap*, many of these checks will be implemented automatically as part of the data entry procedure. Calculations and processes performed by a computer program, including the construction of derived data, will be checked by hand calculations. These checks will also confirm whether the data has been imported into the statistical software correctly and will check any merging of different datasets. Clarification will be sought from the study investigators in the case of discrepancies.

For variables derived from actigraphy (e.g. total sleep time, sleep efficiency), inter-rater reliability on derived variables will be assessed on a sample from 10 overlapping participants each rated independently by two trial investigators.

For each variable, missing value codes will be checked for consistency and proportion of missing values per variable will be presented. Patterns of missing data will be explored. Where missing data imputation is used, imputed values will also be verified using the validation techniques described above.

